#### 2.1.4.3 Laboratory safety variables

Clinical laboratory data consists of blood analysis (including hematology, biochemistry) and urinalysis. Clinical laboratory values will be converted into standard international units and international units that will be used in all listings and tables.

Blood samples for clinical laboratories will be taken as defined in the study flowchart and as clinically indicated. The following laboratory parameters will be analyzed and will be classified as follows:

- Hematology
  - **Red blood cells (RBC) and coagulation:** hemoglobin, hematocrit, RBC, prothrombin time (PT) or international normalized ratio (INR), activated partial thromboplastin time (aPTT),
  - **Platelet count,**
  - **White blood cells (WBC):** WBC with differential, absolute neutrophil count (ANC), lymphocyte count.
- Biochemistry
  - **Metabolism:** fasting glucose, total protein, albumin,
  - **Electrolytes:** sodium, potassium, chloride, calcium, corrected serum calcium, bicarbonate/carbon dioxide, magnesium, phosphate,
  - **Renal function:** serum creatinine, estimated creatinine clearance by MDRD formula, urea or blood urea nitrogen (BUN), uric acid,
  - **Liver parameters:** alanine aminotransferase (ALT), aspartate aminotransferase (AST), alkaline phosphatase, lactate dehydrogenase (LDH), total and direct bilirubin,
  - **Pregnancy test:** female patients of childbearing potential,
- Urinalysis
  - **Quantitative urinalysis** (at baseline only): red blood cells, protein, glucose, pH, ketones, bilirubin, leucocytes,
  - **Qualitative urinalysis** (during treatment period): blood, leukocytes, protein, glucose, ketone, pH, bilirubin,

Technical formulas are described in [Section 2.5.1](#).

#### **2.1.4.4 Vital signs variables**

Vital signs include: heart rate, systolic and diastolic blood pressure, weight and ECOG PS (0, 1, 2, 3, 4).

#### **2.1.4.5 Electrocardiogram variables**

Electrocardiogram assessments will be described as normal or abnormal. An interpretation of the results (normal/abnormal) is to be entered in the eCRF. In case of abnormal result a description of the finding should be reported. If the abnormality meets the definition of TEAE it will also have to be reported as AE.

#### **2.1.4.6 Other safety endpoints**

Other safety endpoints include:

- IR laboratory tests (IPd arm only):
  - Cytokines (TNF- $\alpha$ , IL-1- $\beta$ , IL-4, IL-6, IFN- $\gamma$ ),
  - Markers of complement (C3a, C4, CH50),
  - Serum tryptase.
- Indirect antiglobuline test (IAT)

#### **2.1.5 Pharmacokinetic variables**

The population PK parameters of isatuximab and their inter-patients will be estimated. The effect of pomalidomide, pathophysiological and demographic covariates on main PK parameters will be assessed.

Empirical Bayesian estimation of individual parameters and of individual exposure (Area Under the Curve [AUC]) will also be performed.

Analysis of PK variables will be presented in a separate report.

#### **2.1.6 Immunogenicity**

Human anti-drug antibodies (ADAs) to isatuximab will be assessed during the study as described in the protocol for the IPd arm only and will be analyzed using the ADA population (see [Section 2.3.4](#)).

##### **Periods of observation:**

- ADA pre-treatment period: The ADA pre-treatment period is defined as the time from signed informed consent to the first isatuximab administration.
- ADA on-study observation period: the ADA on-study observation period is defined as the time from first isatuximab administration until the end of the study.

### **ADA attributes:**

- **Pre-existing ADAs** are defined as ADAs that were present in samples drawn during the pre-treatment period.
- **Treatment boosted ADAs** are defined as pre-existing ADA with an increase in titer value between pre-treatment and post-treatment samples of at least two titer steps. Assuming a 2-fold serial dilution schema is used for the study, this means that the post-treatment sample titer value is at least ( $\geq$ ) 4 fold of pre-treatment titer value.
- **Treatment induced ADAs** are defined as ADAs that developed at any time during the ADA on-study observation period in patients without pre-existing ADA, including patients without pre-treatment samples.
- **Transient ADA response** is defined by:
  - Treatment-induced ADA detected only at one sampling time point during the ADA on-study observation period (excluding the last sampling time point) OR,
  - Treatment-induced ADA detected at two or more sampling time points during the on-study observation period, where the first and last ADA-positive samples (irrespective of any negative samples in between) are separated by a period less than 16 weeks and the subject's last sampling time point is ADA-negative.
- **Persistent ADA response** is defined by:
  - Treatment-induced ADA detected at two or more sampling time points during the ADA on-study observation period, where the first and last ADA-positive on-study samples are separated by a period of 16 weeks or longer (irrespective of any negative samples in between),
- **Indeterminate ADA response** is defined by:
  - Treatment-induced ADA detected only the last sampling time point with all prior samples being negative, OR,
  - The last two samples are ADA-positive and separated by a period of less than 16 weeks.

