- q* **Thyroid function tests (TSH, T3 and T4 assessment):** To be performed at baseline and once a year thereafter until EOT or as clinically indicated and at EOT.
- r* **Serum $\beta 2$ -microglobulin:** To be performed at screening.
- s* **Tumor Lysis Syndrome (TLS) markers:** to be done in case of suspicion of TLS (uric acid, creatinine, potassium, phosphate, calcium and corrected calcium).
- t* **Central Labs:** Refer to laboratory manual for sample collection and shipping information.
- u* **Pharmacokinetics (PK; IPd arm only):** Refer to Pharmacokinetics/Pharmacodynamics Flow Chart.

- v **ADA** (Anti-Drug Antibodies [IPd arm only]): To be performed on Day 1 of every cycle prior to each isatuximab administration, Day 15 of Cycle 1, at the EOT visit and at 60 days (± 5 days) after last study treatment administration. At 60 days, if the test is positive or inconclusive, additional ADA samples are required every 30 days (± 7 days) until sample is negative. If isatuximab is stopped prior to pomalidomide and dexamethasone, ADA will be tested on Day 1 of the 2 next cycles. If ADA test at the second cycle administered without isatuximab is positive or inconclusive, ADA testing will be repeated every cycle until negative.
- w **Isatuximab IAR labs**: (TNF- α , IL-1- β , IL-4, IL-6, and IFN- γ) baseline sample to be drawn prior to first isatuximab administration at Cycle 1. Then if a isatuximab infusion associated reaction (IAR) of \geq Grade 2 occurs, additional blood sampling during the AE is required for analysis of cytokine release (TNF- α , IL-1- β , IL-4, IL-6, and IFN- γ), markers of complement activation (C3a, C4, CH50) and serum tryptase.
- x **Bone marrow biopsy/aspirate (as clinically indicated according to site's standard)**.
- At screening: bone marrow aspirate (BMA) will be collected for FISH (including, but may not be limited to, del(17p), t(4;14), t(14;16)) and MRD analyses in central laboratory. BMA or core biopsy (as clinically indicated) will be collected for disease assessment (local laboratory). Central laboratory samples will be collected for all patients but will be analyzed only for randomized patients. If local FISH assessment is done using purified CD138+ plasma cells or by clg FISH, the most recent local FISH report will be collected in patients who fail central laboratory FISH testing, for central review. Baseline MRD sample will be analyzed in patients who achieve a CR.

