## **2.4.7 Analyses of immunogenicity variables**

ADA attributes and response endpoints defined in [Section 2.1.6](#) will be summarized in the ADA population. Titers will be also described using descriptive statistics. Further analyses may be performed, such as time to onset and duration of ADA.

The impact of positive immune response on efficacy, PK and safety endpoints may be further explored by graphical methods or descriptively, depending on ADA prevalence.

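### The SAP's persistent and indeterminate ADA categories can both apply to one patient, and some patients whose last sample is positive fit no category

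*SAP*

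**What the plan says.** SAP 2.1.6 (ADA attributes) gives each category its own conditions.

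- **Transient, route 1:** "Treatment-induced ADA detected only at one sampling time point during the ADA on-study observation period (excluding the last sampling time point) OR"
- **Transient, route 2:** two or more positives, where the first and last positives "are separated by a period less than 16 weeks and the subject's last sampling time point is ADA-negative".
- **Persistent:** two or more positives, "where the first and last ADA-positive on-study samples are separated by a period of 16 weeks or longer (irrespective of any negative samples in between". The last sample may be positive or negative.
- **Indeterminate, route 1:** "Treatment-induced ADA detected only the last sampling time point with all prior samples being negative, OR"
- **Indeterminate, route 2:** "The last two samples are ADA-positive and separated by a period of less than 16 weeks". Nothing is required of earlier samples or of the total span.

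For use of the categories, SAP 2.4.7 says "ADA attributes and response endpoints defined in [Section 2.1.6](#) will be summarized in the ADA population". Neither section ranks one category above another. SAP Table 10 lists ADA at the primary analysis and again at the second interim and final OS analyses.

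Protocol 1.2 (ADA footnote) sets the sampling: "To be performed on Day 1 of every cycle prior to each isatuximab administration, Day 15 of Cycle 1, at the EOT visit and at" a further visit, Day 60 counted from the last study treatment. A positive or inconclusive Day 60 result leads to further samples every 30 days until one is negative. Protocol 1.3 ends ADA sampling for patients still on treatment at amendment 07.

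Protocol 9.3.5.1 defines only transient and persistent, and places positivity at the last sample alone under persistent. SAP Table 1 lists persistent and indeterminate ADA among the definitions updated in version 2, so the departure looks deliberate.

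**The concern.** The three labels are meant to divide patients with treatment-induced ADA, but they are written on different features. Persistent looks at the span between first and last positives. The second indeterminate route looks only at the final two samples. Two conditions on different features can both be true, or both be false, for the same patient.

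What is at stake is the reproducibility of a descriptive table for a listed secondary objective, the immunogenicity of isatuximab. Two programmers following the SAP could report different persistent and indeterminate counts from the same data, and could handle unclassified patients differently. Patients still on treatment at a cut-off have an on-treatment sample as their last, so a positive last sample is a realistic case.

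**Working it through.** The plan states no figure to reproduce, so the check is whether the definitions are exclusive and exhaustive. Let S be the time from first to last positive sample (0 for a single positive).

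**Step 1. Every case, read literally.**

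| Last sample | Other features | Category met |
|---|---|---|
| Negative | One positive | Transient |
| Negative | Two or more positives, S < 16 weeks | Transient |
| Negative | Two or more positives, S ≥ 16 weeks | Persistent |
| Positive | No earlier positive | Indeterminate |
| Positive | Previous sample positive, S < 16 weeks | Indeterminate |
| Positive | Previous sample positive and under 16 weeks earlier, S ≥ 16 weeks | **Persistent and indeterminate** |
| Positive | Previous sample positive and 16 weeks or more earlier | Persistent |
| Positive | Previous sample negative, earlier positive, S ≥ 16 weeks | Persistent |
| Positive | Previous sample negative, earlier positive, S < 16 weeks | **None** |

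With a negative last sample the rules work. Both faults need a positive last sample.

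**Step 2. Spacing of planned samples.** Cycles last 28 days. Assume the last study dose is on Day 22 of the last cycle and end of treatment is 30 days later. The longest planned gap is then from Day 1 of the last cycle (Cycle 2 or later) to end of treatment: 21 + 30 = 51 days, or 51/7 = 7.3 weeks. The under-16-weeks condition on the final pair is always met on schedule.

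**Step 3. Examples (weeks from Cycle 1 Day 1).**
- *Overlap:* positive at weeks 2, 4, 8, 12, 16, 20 and 24, then a cut-off. S = 24 − 2 = 22 weeks, so persistent. The last two samples are 24 − 20 = 4 weeks apart, so indeterminate as well.
- *Gap:* negative at week 2, positive at 4, negative at 8, positive at 12, then a cut-off. S = 12 − 4 = 8 weeks. Not transient (last sample positive), not persistent (S < 16), not indeterminate (an earlier positive, and the final pair is not both positive).

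**Step 4. Where the overlap starts.** Take a patient positive at every planned post-dose sample from Cycle 1 Day 15 to Day 60, treated for c cycles. S = 4(c − 1) + 3 + 60/7 − 2 weeks.
- c = 1: S = 9.6, indeterminate only.
- c = 2: S = 13.6, indeterminate only.
- c = 3: S = 17.6, persistent and indeterminate.

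**Step 5. Enumeration.** The schedule is Cycle 1 Day 15, Day 1 of Cycles 2 to c, end of treatment and Day 60, for c = 1 to 10. That is c + 2 samples, so the number of patterns with at least one positive is the sum of (2^(c+2) − 1) = 8,174.

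| Outcome | SAP as written | With the fix below |
|---|---|---|
| Persistent only | 5,688 | 5,688 + 2,008 = 7,696 |
| Persistent and indeterminate | 2,008 | 0 |
| Transient only | 402 | 402 |
| Indeterminate only | 48 | 48 + 28 = 76 |
| None | 28 | 0 |
| Total | 8,174 | 8,174 |

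These count possible patterns, not patients. The enumeration stops at Day 60 even when that sample is positive, so it does not follow the repeat-until-negative rule.

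**The case against.** The strongest reply is that the sampling plan mostly prevents the problem. A positive or inconclusive Day 60 sample is repeated until negative, so a patient who completes follow-up should end on a negative sample, where the categories work. This stands, and it narrows the point. It does not remove it: a data cut-off, death, withdrawal, or the end of sampling under amendment 07 can leave a positive last sample.

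A second reply is that an indeterminate response, in ordinary use, is one that cannot yet be called transient or persistent, so a span already at 16 weeks would be taken as persistent. That is sensible, but the SAP does not say it. Reading the second indeterminate route as requiring the last two samples to be the only positives also removes the overlap. Those words are absent, whereas the first route does require all prior samples to be negative. That reading also raises the unclassified patterns from 28 (1 + 3 × 9) to 56 (2 + 6 × 9).

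The protocol is no fallback. Its own definitions leave the Step 3 gap patient unclassified.

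A reader might infer three stronger things, and the documents do not support them:
- *That every always-positive patient is in both categories.* Step 4 shows that a span under 16 weeks gives indeterminate only.
- *That everyone positive at the last two samples is affected.* Those with a span under 16 weeks are classified cleanly, and the gap patients are negative at the next-to-last sample.
- *That the SAP directs the clearest persistent pattern to be reported as indeterminate.* It gives no order, so this is a possible result of programming, not an instruction.

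**Conclusion.** The definitions are wrong as written, in a limited way. The overlap covers patients whose last two samples are positive and under 16 weeks apart, with a first-to-last positive span of 16 weeks or more. The gap covers patients with a positive last sample, a negative next-to-last sample, an earlier positive and a span under 16 weeks. Both arise only when the last available sample is positive.

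The consequence is minor. Only the descriptive transient, persistent and indeterminate counts in the IPd arm change. ADA incidence, prevalence and negative status (SAP 2.1.6, ADA response endpoints) do not use the split, and no efficacy test does. The optional exploration of impact in SAP 2.4.7 refers to positive immune response, not to these classes.

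The number of patients cannot be stated, because neither document gives an ADA rate or the share of patients ending on a positive sample. The pattern counts show that the faults occur on the planned schedule and should not be read as frequencies. The conclusion rests on a literal reading. The Day 22 last-dose assumption affects only the spans and pattern counts.

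**What to change.** In SAP 2.1.6, replace both indeterminate routes with one: treatment-induced ADA where the last sample is positive and the first and last positive samples are under 16 weeks apart, including a single positive at the last sample. Leave transient and persistent as written. Step 5 shows that every overlap pattern then becomes persistent only, every gap pattern becomes indeterminate, and nothing else moves.

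Add a note that these definitions supersede protocol 9.3.5.1, which has no indeterminate category and counts positivity at the last sample alone as persistent. Without it the two documents still differ on those patients.

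The cost is one redefining sentence, one note and the matching programming change. No new data are needed, and no hypothesis test changes. If ADA has already been tabulated at an earlier analysis, the split should be re-run under the new rule so that later tables are comparable.

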### **ADA response endpoints:**

- **ADA negative patients** are patients without any treatment induced or treatment boosted ADA during the on-study observation period.
- **ADA incidence** is defined as proportion of **ADA positive patients**, ie, patients with at least one treatment induced or treatment boosted ADA at any time during the on-study observation period.
- **ADA prevalence** is defined as proportion of all patients tested positive for ADAs (including preexisting ADAs, treatment boosted ADAs and treatment induced ADAs) at any time point.

#### **2.1.7 Health-related quality-of-life endpoints**

Health-related quality of life (HRQL) will be assessed using the European Organization for Research and Treatment of Cancer Quality of Life Questionnaire – Cancer specific module with

30 items (EORTC QLQ-C30) and the EORTC QLQ myeloma-specific module with 20 items (MY20). Health status and health utility will be assessed using the EuroQol measure with 5-dimensions and 5-levels per dimension EQ-5D-5L (2,3,4,5,6).

The QLQ-C30 incorporates a Global Health Status/QoL scale, five functional scales (Physical functioning [PF2], Role functioning [RF2], Cognitive functioning [CF], Emotional functioning [EF] and Social functioning [SF]), three symptom scales (Fatigue [FA], Pain [PA] and Nausea/Vomiting [NV]) and six additional single items (Dyspnoea [DY], Insomnia [SL], Appetite Loss [AP], Constipation [CO], Diarrhoea [DI] and Financial Difficulties [FI]) as symptoms commonly reported by cancer patients and the perceived financial impact of the disease.

The EORTC QLQ-MY20 (MY20) is meant for use among patients with multiple myeloma cancer and comprised of:

- 2 functional subscales (body image, future perspective), (higher scores better = greater functionality).
- 2 symptoms scales (disease symptoms and side-effects of treatment) (higher scores worse = more symptomatic).

Raw scores (RS)/scores for the EORTC are calculated using EORTC QLQ-C30 and EORTC QLQ-MY20 scoring formulas (detailed in [Appendix F](#)):

- RS is the mean of the component items.
- For the Functional scales:  $\text{Score} = [1 - ((\text{RS} - 1) / \text{range})] \times 100$ .
- For Symptom scales / single items scales and the Global health status/QoL scale:  $\text{Score} = [(\text{RS} - 1) / \text{range}] \times 100$ .

The range is the difference between the maximum and the minimum response to individual items.

The EQ-5D-5L incorporates the EQ-5D descriptive system and a visual analogue scale (VAS).

The EQ VAS records the respondent's self-rated health on a 20 cm vertical, visual analogue scale with endpoints labelled 'the best health you can imagine' and 'the worst health you can imagine'. This information can be used as a quantitative measure of health as judged by the individual respondents.

The EQ-5D-5L descriptive system comprises the following 5 dimensions: mobility, self-care, usual activities, pain/discomfort and anxiety/depression. Each dimension has 5 levels: no problems, slight problems, moderate problems, severe problems and extreme problems.

For EQ-5D-5L, VAS will be described as given by patient and health utility index will be calculated according to EuroQol specific country algorithms. In case a specific country algorithm is missing the value sets based on the UK population will be used to generate health utility scores.

Rules of handling with missing items are detailed in [Appendix F](#) for the EORTC questionnaires while missing values are treated in the Crosswalk value sets for the EQ-5D-5L.

## 2.1.8 Exploratory biomarker analysis

### 2.1.8.1 Immune Genetic Determinants

A blood sample will be collected at Day 1 of Cycle 1. Leukocyte DNA will be extracted and analyzed for immune genetic determinants (such as FcγR polymorphisms, HLA and KIR genotypes) and correlated with parameters of clinical response.

Germline genetic data of FcγR, HLA and KIR genes will be analyzed on blood samples collected on D1 of Cycle 1:

- FCGR polymorphisms (FCGR2A and FCGR3A): For each gene, the results will be of the form AA, Aa or aa with A and a-alleles, the major and minor allele, respectively.
- HLA genotypes: HLA-A, HLA-B and HLA-C have been typed (see [Table 5](#)).

**Table 5 - Epitopes of HLA Class I recognized by KIR**

HLA class I	Epitope	Amino-acid at position a					Associated allotypes
		77	80	81	82	83	
HLA-B	Bw6	Ser	Asn	Leu	Arg	Gly	
	Bw4	Asn	Thr	Ala	Leu	Arg	
	Bw4	Asn	Ile	Ala	Leu	Arg	
	Bw4	Asp	Thr	Leu	Leu	Arg	
	Bw4	Ser	Thr	Leu	Leu	Arg	
	Bw4	Ser	Thr	Ala	Leu	Arg	
HLA class I	Epitope	77	80	81	82	83	
HLA-A	Aw4	Asn	Ile	Ala	Leu	Arg	A*23; A*24
	Aw4	Ser	Ile	Ala	Leu	Arg	A*32
	A3	Key residues not yet published					A*03
	A11	Key residues not yet published					A*11
HLA class I	Epitope	77	80				
HLA-C	C1	Ser	Asn				
	C2	Asn	Lys				

a Numbering from the first codon of the mature protein

- KIR genotypes: The presence or absence of 16 KIR genes will be screened. A KIR gene will be defined as present if at least one assay gives positive results; otherwise it will be defined as negative.

Results of immune genetic determinants analyses will be presented in a separate report.

In addition, samples (serum) will be collected to evaluate the potential isatuximab interference with the M protein assessment in immunoelectrophoresis and immunofixation assays. These additional samples will be collected at all time-points that M protein is analyzed for patient treated in IPd arm.

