### **2.3.5 Biomarker population**

The analysis population for immune genetic biomarkers will be defined as the set of patients from ITT population evaluable for at least one of the genetic biomarkers

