#### *2.4.8.1.2 Univariate analysis*

Each genetic biomarker will be tested for a potential prognostic/predictive effect for PFS.

A cox regression model will be conducted separately for each genetic biomarker with a treatment effect, a biomarker effect and a biomarker×treatment interaction.

For biomarkers coded as genotype (0, 1, 2), different coding may be investigated: additive, dominant or recessive.

Benjamini-Hochberg multiple correction procedure will be used to control the False Discovery Rate.

Additional analyses using ORR and OS instead of PFS might also be performed.

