### 2.5.3 Missing data

The analyses and summaries of continuous and categorical variables will be based on observed data only. Percentages will be calculated using as denominator the number of patients with non-missing observation in the considered population. When relevant, the number of patients with missing data is presented.

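### Read literally, the SAP's KIR rule scores a failed or missing assay as gene absence, and the observed-data rule does not clearly prevent this

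*SAP*

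**What the plan says.** Four parts of the SAP bear on this.

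- **Coding (2.1.8.1, text after Table 5).** "The presence or absence of 16 KIR genes will be screened". The rule for each gene is then: "A KIR gene will be defined as present if at least one assay gives positive results; otherwise it will be defined as negative". Its wording allows for more than one assay per gene.
- **Population (2.3.5).** The immune genetic analysis uses "the set of patients from ITT population evaluable for at least one of the genetic biomarkers". One usable FCGR, HLA or KIR result is enough to qualify.
- **Model (2.4.8.1.2).** "A cox regression model will be conducted separately for each genetic biomarker with a treatment effect", a biomarker effect and their interaction, with PFS as the outcome. The section does not limit each model to patients with a usable result for that marker. It adds: "Benjamini-Hochberg multiple correction procedure will be used to control the False Discovery Rate".
- **Missing data (2.5.3).** "The analyses and summaries of continuous and categorical variables will be based on observed data only", with percentages taken over patients whose value is not missing.

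The genetic analysis serves an exploratory objective (1.2.3) and goes to a separate report (2.1.8.1). Table 10 places the biomarker analysis at the primary PFS analysis.

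**The concern.** Under the KIR rule, *otherwise* covers three different states: all assays valid and negative; one negative and another failed; and no valid result at all. Only the first shows that the gene is absent. The other two are unknown, yet the literal rule gives all three the same code.

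The SAP separates unknown from negative elsewhere. Cytogenetic risk has an unknown/missing level (2.1.1). R-ISS leaves patients with inconclusive FISH unclassified unless stage III can be settled without it (Table 3). A missing baseline Coombs result is counted separately (2.4.5.6). A questionnaire scale with too few answers is set to missing (Appendix F). The clinical subgroup analyses are confined to patients with results (2.4.4.1.2). Among the genetic markers, only KIR is given a default value.

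If carriers are coded as absent, carrier frequency is understated and the reference group in the Cox model is diluted. When failure is unrelated to outcome, the marker and marker-by-treatment effects shrink toward the null, and true signals become harder to detect after the false-discovery correction. When failure is related to sample quality or site, the bias could go either way.

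**Working it through.** The documents give no figure to reproduce: no sample size, alpha or event count depends on this rule. The check is a reading of the text followed by an illustration on assumed inputs.

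**Reading.** Take a patient with a valid FCGR result whose assays for one KIR gene all failed.

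1. Section 2.3.5: the patient is included, through FCGR.
2. Section 2.1.8.1: no assay is positive, so the gene is coded negative.
3. Section 2.4.8.1.2: the model for that gene has no further restriction, so the patient enters as a non-carrier.
4. Section 2.5.3: if applied to the raw assay results, it removes the patient. If applied to the derived variable, there is no missing value left to remove. The SAP does not say which.

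**Inputs for the illustration.** p is the true carriage of the gene. f is the share of *included* patients with no valid result for that gene. Neither is in the documents, so both are assumed. N = 300 is the planned enrolment (SAP 1.3), used only for scale; the biomarker population may be smaller. Failure is taken to be independent of carriage.

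**Formula.** Misclassified share of the absent group = f·p / ((1 − p) + f·p).

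| f | p = 0.50 | p = 0.80 | p = 0.95 |
|---|---|---|---|
| 2% | 0.010/0.510 = 2.0% | 0.016/0.216 = 7.4% | 0.019/0.069 = 27.5% |
| 5% | 0.025/0.525 = 4.8% | 0.040/0.240 = 16.7% | 0.0475/0.0975 = 48.7% |
| 10% | 0.050/0.550 = 9.1% | 0.080/0.280 = 28.6% | 0.095/0.145 = 65.5% |

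In patients per 300 at f = 5%: with p = 0.50, 300 × 0.05 × 0.50 = 7.5 carriers join 150 true non-carriers. With p = 0.95, 300 × 0.05 × 0.95 = 14.25 carriers join only 15 true non-carriers.

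**Effect on a hazard ratio.** Assume a true carrier HR of 0.60. A rough approximation is 0.60 raised to the power (1 − misclassified share). A simulation of 60,000 patients checked it (exponential times, censoring at a fixed time, Cox model with the marker only).

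| p | f | Approximation | Simulated, literal rule | Simulated, unknowns excluded |
|---|---|---|---|---|
| 0.50 | 5% | 0.615 | 0.617 | 0.604 |
| 0.50 | 10% | 0.629 | 0.612 | 0.587 |
| 0.95 | 5% | 0.770 | 0.756 | 0.585 |
| 0.95 | 10% | 0.838 | 0.823 | 0.596 |

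Excluding the unknowns returns the HR to about 0.60. The simulation had no treatment arm, so it shows dilution of the marker effect and gives no figure for the interaction.

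**The case against.** The best defence is that the KIR sentence only says how to combine results that exist. A failed or unrun assay is not a result, and 2.5.3 already confines categorical analyses to observed data. On that reading nobody is miscoded.

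Three further points support the defence. FCGR, HLA and KIR are all typed on DNA from the Cycle 1 Day 1 blood draw (SAP 2.1.8.1; Protocol 9.4.2). A patient with no sample or unusable DNA would have no usable marker and would fall outside 2.3.5, so f counts only KIR-specific failure and may be well below the overall missing rate. The large percentages need p near 0.95, where only about 15 of 300 patients are true non-carriers and estimates would be imprecise even with perfect coding. And the analysis is exploratory.

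These three points stand, and they limit the size and the severity. The appeal to 2.5.3 stands only in part. It is a possible reading, but the KIR sentence states a default without a validity condition, and once that default is applied the missing value has gone. Nor does the SAP define what makes a KIR gene evaluable. Two programmers could build different datasets and each cite the SAP.

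**Conclusion.** The rule, followed as written, gives a wrong code to a limited group: patients in the biomarker population through another usable marker, including other KIR genes, whose assays for the gene in question failed or are missing without a positive result. It is not reconciled with 2.5.3.

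A reader might infer that every patient with failed or missing KIR assays does enter the models as a non-carrier, and that reported carrier frequencies are therefore too low. The documents do not support that. Patients with no usable genetic result are excluded, 2.5.3 may have been meant to take precedence, and nothing shows that any KIR-specific failure occurred.

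The size is unknown. On the assumed values the effect is small at moderate carriage (p = 0.50, f = 5%: about 5% of the absent group, HR 0.60 moving to about 0.62). It is material mainly for near-universal genes (p = 0.95, f = 5%: about 49%, HR moving to about 0.76 to 0.77). PFS, ORR and OS testing are untouched. Severity: minor.

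**What to change.** In SAP 2.1.8.1, code each KIR gene as:

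- **present** if any assay is positive;
- **absent** only if all assays for that gene gave valid results and all are negative;
- **missing** if none is positive and any assay failed or is missing.

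The third line is needed to settle the mixed case of one negative and one failed assay.

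In 2.4.8.1.2, fit each marker's model in patients with a non-missing result for that marker, and report the number missing per marker.

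Table 1 shows that SAP version 3 postdates the primary PFS analysis, and Table 10 ties the biomarker analysis to it, so the analysis may already have been run. If so, confirm which coding was used and recode if needed.

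The cost is a few lines of SAP text, a recode, and a slightly smaller N for some KIR genes. One side effect should be noted in the report: a partly failed gene is kept when another assay is positive but dropped when the rest are negative, so carrier frequency could be slightly overstated if partial failures are common.
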